To investigate the long-term changes in psychosocial well-being in children living with obesity after participation in one of two multifactorial family-centered lifestyle interventions. Furthermore, to compare this alteration in psychosocial well-being between the intervention groups and with a reference group of children who were never invited to participate in the interventions. Also, we aim to investigate the effect that is not caused by the weight change by adjusting for this.

Methods:

Design:

This observational cohort study includes children living with obesity in two municipalities in Denmark between August 1st, 2014, and June 30th, 2020. The children were followed until February 1st, 2023, with questions from the Danish National Well-being Questionnaire (DNWQ) obtained from the Danish agency for IT and Learning (STIL), The ministry of Education (19).

Participants:

Children in the intervention groups were 5 to 10 years of age and participated in one of two different family-centered intervention: a one-year intervention and a three-year intervention. Children with obesity living in one of the municipalities and who were never invited to participate in the interventions will act as a reference group for this study.

Obesity is defined by the International Obesity Task Force (IOTF) guideline as a $BMI \geq 30 \text{ kg/m}^2$ adjusted for age and sex (20). If a child's BMI (adjusted for age and sex) was above this cut-off, the parents were notified, and the family invited to participate in the intervention. After acceptance from the parents, the child was referred to the intervention.

Inclusion criteria:

- Inclusion visit between August 1st, 2014, and June 30th, 2020 (figure 1).
- Obesity at time of referral as defined by the IOTF guideline (20).
- Age between 5 and 10 years at inclusion visit.

- A completed DNWQ within a timeframe of 10 months prior to 2 months after inclusion.
- A completed DNWQ at follow-up (1 to 3 years after inclusion visit).

Exclusion criteria:

- Children declining participation in a community-based lifestyle intervention.

The groups

- Two intervention groups:
 - Children with obesity attending the one-year intervention.
 - Children with obesity attending the three-year intervention.
- Non-intervention group/reference group: children with obesity who were not invited to the interventions.

Outcome:

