The outcome of the study will be the children's answers to specific questions from the DNWQ regarding the psychosocial well-being related to school. The DNWQ is a national questionnaire used to examine how primary school-children perceive their well-being and learning environment in school. For the children in 0th to 3rd grade, the questionnaire consists of 20 questions where the children express their level of agreement with each question using a three-point Likert scale, ranging from 1 to 3. For children and adolescents in 4th to 9th grade, the questionnaire consists of 40 questions where the level of agreement with each question is rated on a five-point Likert scale, ranging from 1 to 5. The DNWQ is completed annually from January 20th to March 20th and is an integrated part of the teaching for all school children in public primary schools, including special schools and treatment centers. The DNWQ was introduced in 2015.

We selected four primary and three secondary questions as representative of psychosocial well-being. Our focus will be on the four primary questions. The answers at time of inclusion and follow-up will be included in the analyses. At follow-up the answers of the questionnaire completed closest to two years from the time of inclusion, will be prioritized.

All the questions will be dichotomized into: High well-being / Low well-being. Responses 1 and 2 for grades 0-3 and response 1-3 for grades 4-9 will be characterized as low well-being.

Primary outcomes:

The following four questions have been selected as our primary outcomes

1. Question:

Are you happy with your school?

2. Questions:

Do you feel lonely at school? (0-3 grade)

Do you feel lonely? (4-9 grade)

3. Question:

Is anyone teasing you so that you feel sad? (0-3 grade)

Have you been bullied this school year? (4-9 grade)

4. Question:

Does your stomach ache when you are at school? (0-3 grade)

How often does your stomach ache? (4-9 grade)

Secondary outcomes:

The following three questions has been selected as our secondary outcome

A. Question:

Are you good at solving your problems? (0-3 grade)

How often can you find a solution to problems, just by trying hard enough? (4-9 grade)

B. Question:

Can you concentrate during class?

C. Question:

Are you good at helping each other in class? (0-3 grade)

Most students in my class are friendly and helpful. (4-9 grade)

Data sources and study variables:

Data sources:

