Firstly, the McNemar test will be used to investigate potential change in psychosocial well-being from time of inclusion to follow-up for each of the dichotomized Questions 1-4 (primary outcome) and Questions A-C (secondary outcomes) in both intervention groups. All questions will be dichotomized into: high well-being/low well-being.

Secondly, a crude and an adjusted logistic regression analysis will be conducted to compare the change in psychosocial well-being between children in the intervention group and the non-intervention group and between the two intervention groups.

The multivariable model will be adjusted for no more than 1 co-variate per 10 observations of the least common outcome.

The co-variates are listed in prioritized order: 1) Inclusion outcome, 2) BMI z-score, 3) age at inclusion 4) sex, 5) highest completed household education, 6) immigration status, 7) disposition for mental illness, 8) mental illness, and 9) family structure.

As an explorative outcome, a logistic regression model adjusted for change in BMI z-score (from inclusion to follow-up) will be performed to remove the potential effect of weight change on the association between exposure and change in psychosocial well-being based on the primary outcomes (Questions 1-4). The BMI z-score observed closest to the included DNWQ at follow-up will be used.

We wish to investigate the stratified effect of BMI z-score, parental level of education, immigration status and disposition for mental illness before we examine their potential for effect modification for the change in psychosocial well-being for each of the primary questions. These analyses will be conducted across comparisons of each intervention group with the non-intervention group and between the two intervention groups.

Figure 1: Lexi diagram for time of inclusion (x-axis), inclusion age of the participants (y-axis), and time points for the DNWQ.

[figure not shown]

Table 1: Characteristics at time of inclusion, divided by groups:

	One- year Intervention (n =)	Three-year Intervention (n =)	Non- Intervention (n =)
Age (year) at inclusion			
Sex, n (%)			
Boys			
Girls			
BMI z-score			
Highest completed household education, n (%)			
Short			
Middle			
Long			
Family type, n (%)			
Single caretaker			
Non-single caretaker			
Immigration status, n (%)			
Danish origin			
Immigrants			
Parental mental illness (yes), n (%)			
Psychiatric diagnosis, child (yes), n (%)			

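### The within-group McNemar tests, planned only in the two intervention groups, pool the 3-point and 5-point questionnaire forms, so a change of form or ageing can be read as a change in well-being

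*Combined protocol and SAP*

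**What the plan says.** Statistics, first analysis step: McNemar tests for change "from time of inclusion to follow-up for each of the dichotomized Questions 1-4 (primary outcome) and Questions A-C (secondary outcomes) in both intervention groups". The McNemar rows of Tables 3 and 4 accordingly list the one-year and three-year interventions and no reference group.

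Outcome section: the grade 0-3 form has a 3-point scale and the grade 4-9 form a 5-point scale. Both are reduced to High/Low by form-specific cuts: "Responses 1 and 2 for grades 0-3 and response 1-3 for grades 4-9 will be characterized as low well-being". Questions 1 and B have one wording for all grades. Questions 2, 3, 4, A and C have two. In Question 3, for example, younger children are asked about teasing that makes them sad, older children about bullying in the current school year. In Question 4 the older version drops the school setting.

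Timing:
- Age: "Age between 5 and 10 years at inclusion visit".
- Baseline answer: "A completed DNWQ within a timeframe of 10 months prior to 2 months after inclusion".
- Rounds: "The DNWQ is completed annually from January 20th to March 20th".
- Follow-up answer, within 1 to 3 years of inclusion: "At follow-up the answers of the questionnaire completed closest to two years from the time of inclusion, will be prioritized".

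Table 2 gives High/Low percentages at both times for all three groups. The logistic models (Tables 3 and 4) regress the follow-up answer on group and the inclusion answer. Model 2 adds age at inclusion and other covariates.

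**The concern.** McNemar's test compares the share with low well-being at two times in the same children. It reads as change in well-being only if both answers measure the same thing. For a child who moves from grade 3 or below to grade 4 or above, the scale and the cut change, and for five items so does the question. The plan offers no evidence that two of three categories and three of five mark the same level of well-being. Any difference between forms goes straight into the discordant pairs, and the test has no covariates to absorb it.

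The Objective section opens with long-term change after participation, and the McNemar odds ratios and p-values head Tables 3 and 4. A significant result there, in either direction, could be reported as change following the intervention when it reflects the form, ageing, or both.

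**Working it through.** The documents give no sample size, prevalence, grade mix or form effect, so there is no planned figure to reproduce. The timing rules come from the documents; everything marked *assumed* does not.

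**1. Rounds between the paired answers.** Take each inclusion date from 1 August 2014 to 30 June 2020, with rounds from 2015 up to 1 February 2023. Choose the baseline round within -10 to +2 months and the follow-up round closest to two years within 1 to 3 years. If inclusion dates are spread evenly over the calendar (*assumed*), the gap is two rounds for about 70% of dates and three for about 30%: 70.5/29.5% with the round on 20 January, 70.3/29.7% on 19 February, 69.1/30.9% on 20 March. The split depends on the season of inclusion. With a 19 February round, all January-July dates give two rounds and all September-November dates give three. If the preferred round is missing, a one-round gap is possible for about 18% of dates.

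**2. Who changes form.** Assume one grade per year. At a two-round gap, baseline grades 2 and 3 switch; at three rounds, grade 1 does too; at one round, only grade 3. Hence, with even inclusion dates,

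switching share = 0.299 × P(grade 1) + P(grade 2) + P(grade 3).

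| Baseline mix over grades 0-4 (*assumed*) | Switching share |
|---|---|
| 60/30/4/2/4% | 0.090 + 0.04 + 0.02 = 15% |
| 50/30/10/5/5% | 0.090 + 0.10 + 0.05 = 24% |
| 20% each | 0.060 + 0.20 + 0.20 = 46% |
| 15/25/30/20/10% | 0.075 + 0.30 + 0.20 = 57% |

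Season matters here too. The first mix gives 0.04 + 0.02 = 6% if every gap is two rounds and 0.30 + 0.06 = 36% if every gap is three.

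**3. Effect on McNemar with no true change.** *Assumed*: low well-being of 50% on the younger form and 40% on the older, and latent bivariate-normal answers with correlation 0.4. Let b be low-to-high pairs and c high-to-low pairs; the statistic is (b - c)²/(b + c). The expected value of (b - c)/n is the switching share times the form effect, 0.46 × 0.10 = 0.046 for the even mix.

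Cell probabilities: switchers 0.2367 (b) and 0.1367 (c); same-form children on the younger form 0.1845 each way, on the older form 0.1779 each way. With 34% staying on the younger form, 20% staying on the older and 46% switching:
- b: 0.34 × 0.1845 + 0.20 × 0.1779 + 0.46 × 0.2367 = 0.207
- c: 0.34 × 0.1845 + 0.20 × 0.1779 + 0.46 × 0.1367 = 0.161
- spurious odds ratio c/b = 0.78

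At n = 400 the noncentrality is about (400 × 0.046)²/(400 × 0.368) = 2.3, whose square root is 1.52. The chance of rejection is about P(Z > 1.96 - 1.52) = 33%, which agrees with the simulation (4,000 replicates, asymptotic test):

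| Switching | 50 vs 40%, n = 100/200/400 | 50 vs 45%, n = 100/200/400 |
|---|---|---|
| 15% | 5.4 / 6.3 / 7.7% | 5.3 / 5.5 / 5.4% |
| 24% | 5.8 / 9.0 / 13.2% | 4.9 / 6.5 / 6.7% |
| 46% | 11.8 / 19.2 / 32.9% | 6.6 / 8.6 / 11.9% |
| 57% | 15.2 / 27.0 / 47.3% | 7.5 / 11.6 / 16.5% |

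Repeat runs moved these by about one percentage point, so the 46% row is quoted as 11-33%. Reversing the forms (40 vs 50%) gives similar rates with the opposite sign. With no form effect the rate is about 5%. The exact test is slightly lower (8.8 / 16.3 / 30.3% at 46% switching).

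**4. Between-group models.** With no true effect and the same form mix in both groups, the simulated odds ratio is 1.00.

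**The case against.** The best defence has four parts.

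- *The plan already harmonises the forms.* The cuts are form-specific and both place the middle category in Low. True, but this is a convention. Nothing shows that it equates the forms, and it cannot undo a change in the question.
- *The reference group's shift is already planned output.* Table 2 gives the margins that McNemar compares. This stands in part: a reader can see a shared shift, but without a test, an interval or a split by form. A McNemar row for the reference group would itself reflect form and ageing together, so it cannot isolate the form effect.
- *The size is unknown.* This stands in full. The larger rates need about half the children to switch and a 10-point form effect. With few switchers or a small effect the inflation is slight. The 70/30 split is itself an assumption about inclusion dates.
- *The group comparison is made by the logistic models, with a reference group answering the same forms.* This also stands.

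On the last point, a reader might go further and infer that the between-group odds ratios are biased as well. The documents do not support that. A bias needs a form mix that differs between groups, and nothing in the plan points to one. With imposed imbalances and a 10-point form effect, the null odds ratio moved to 1.05 (1.11 after adding age) in a deliberately extreme case, 0% against 40% on the older form at inclusion. It moved to 0.87 (0.96 after adding age) with 44% against 79% on the older form at follow-up. These cases justify reporting form by group, not changing the main models.

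**Conclusion.** The concern holds for the within-group McNemar tests. That some children change form follows from the age range, the annual rounds and the follow-up rule. That the test cannot separate form change and ageing from real change follows from its being unadjusted, unsplit by form and run only in the intervention groups.

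Size and direction are unknown. As illustrations resting on the assumed correlation, grade mix, inclusion dates and n = 100 to 400, a nominal 5% test rejects in about 5-8% of samples at 15% switching and 11-33% at 46% switching for a 10-point form effect, and in about 5-12% over the same switching shares for a 5-point effect. A reader might infer that the tests will show false improvement; the documents give no basis for either direction. The between-group models are unaffected when the form mix is equal across groups. The change is worth making because it is cheap, not because a large bias has been shown.

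**What to change.** 1. Add a non-intervention McNemar row to Tables 3 and 4. State that within-group results are not attributed to the intervention and that their p-values are not compared across groups, since the between-group models make that comparison. Note that the new row reflects form and ageing together.
2. As a sensitivity analysis, repeat McNemar in children who answered the same form both times, reported with its n and age. This removes the form change but not ageing.
3. Report form (grades 0-3 or 4-9) at inclusion and at follow-up by group. Only if it differs materially, add form at both times to models 1 and 2 as a sensitivity analysis. The main models, the covariate order and the limit of one covariate per 10 observations of the rarer outcome stay unchanged.

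Cost: SAP wording, a few table rows and one or two sensitivity analyses. No new data are needed, because grade determines the form. The same-form subset is smaller (about 85% of a group at 15% switching, 54% at 46%) and has a different age mix. Three within-group p-values side by side invite comparison, which is why the statement in item 1 is needed. Form terms, if used, will be correlated with age.

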^bLogistic regression model with the groups as the independent variable, the follow-up outcome as the dependent variable, and the following covariates: inclusion outcome, age, BMI z-score, sex, highest completed household education, immigration status, disposition for mental illness, mental illness (child), and family structure.

OR: odds ratio; CI: confidence interval.

Table 4: McNemar's test and logistic regression analyses for the secondary outcomes comparing the change in psychosocial well-being between intervention and non-intervention group:

	Question A	Question B	Question C
	OR (95% CI), p-value	OR (95% CI), p-value	OR (95% CI), p-value
McNemar's			
One-year intervention			
Three-year intervention			
Logistic regression model 1 ^a			
One-year vs Non-intervention			
Three-year vs Non-intervention			
Three-year vs. one-year intervention			
Logistic regression model 2 ^b			
One-year vs Non-intervention			
Three-year vs Non-intervention			
Three-year vs. one-year intervention			

^aLogistic regression model with the groups as the independent variable, the follow-up outcome as the dependent variable, and adjusted for the co-variable: inclusion outcome.

^bLogistic regression model with the groups as the independent variable, the follow-up outcome as the dependent variable, and the following covariates: inclusion outcome, age, BMI z-score, sex, highest completed household education, immigration status, disposition for mental illness, mental illness (child), and family structure.

OR: odds ratio; CI: confidence interval.

Table 5: Effect modification analyses of the primary outcomes comparing the change in psychosocial well-being between the one-year intervention and non-intervention groups.

Subgroup	Number of children			aOR (95% CI for the primary outcomes)				P-value for interaction
	Total	Non-intervention	One-year intervention	Q1	Q2	Q3	Q4	
BMI z-score								
< 3								
> 3								
Highest completed household education								
Shorter								
Longer								
Parental mental illness								
Yes								
No								
Immigration status								
Danish origin								
Immigrants								
Full population								

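### No covariate captures calendar time, although eligible DNWQ rounds run from 2015 to early 2023, so confounding of the between-group odds ratios by period cannot be excluded

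*Combined protocol and SAP*

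**What the plan says.** The Design section describes an observational cohort that "includes children living with obesity in two municipalities in Denmark between August 1st, 2014, and June 30th, 2020". On follow-up it says: "The children were followed until February 1st, 2023". The Outcome section gives the timing of the questionnaire: "The DNWQ is completed annually from January 20th to March 20th", and "The DNWQ was introduced in 2015". A child needs a baseline questionnaire between 10 months before and 2 months after inclusion, and a follow-up questionnaire 1 to 3 years after it. The follow-up round nearest to two years takes priority.

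The Statistics section ranks the covariates: "The co-variates are listed in prioritized order: 1) Inclusion outcome, 2) BMI z-score, 3) age at inclusion 4) sex", followed by household education, immigration status, disposition for mental illness, the child's own mental illness and family structure. The model 2 footnotes to Tables 3 and 4 name the same nine: "inclusion outcome, age, BMI z-score, sex, highest completed household education, immigration status, disposition for mental illness, mental illness (child), and family structure". Tables 5-7 use these nine, less the one stratified on. The number of covariates is capped at one per 10 observations of the rarer outcome.

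Under Participants, the groups are defined by the programme attended or by never having been invited. Invitation is described as following from a BMI above the cut-off. Under Data sources, the reference group is drawn from TM-Sund, one of the two municipal record systems.

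**The concern.** Happiness with school, loneliness, teasing or bullying, and stomach ache can change between survey rounds for reasons unrelated to obesity care. If one group's follow-up answers come more from later rounds than another's, such a change enters the odds ratio and looks like an intervention effect.

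The planned covariates do not remove this. The inclusion outcome accounts for where a child started, not for a general shift between that child's baseline and follow-up rounds. Age at inclusion does not stand in for year, because a child aged 5 to 10 can enter in any year. No matching on time and no sensitivity analysis by period is described. The Table 1 shell has no row for inclusion year or round, so that table would not show an imbalance.

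Three omissions leave the calendar mix of the groups undetermined: no start or stop dates for either programme, no reason why children above the cut-off were not invited, and no definition of an inclusion visit for children who were never invited.

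**Working it through.** The plan states no sample size, outcome rate or distribution of the groups over time, so it has no figure of its own to reproduce. Three checks were made.

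**1. Which rounds can count.** Inputs, all from the plan: inclusion 1 Aug 2014 to 30 Jun 2020; rounds 20 Jan to 20 Mar from 2015; end of follow-up 1 Feb 2023; the two windows above.

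- Earliest usable inclusion: the 2015 round opens on 20 Jan 2015 and must lie within 2 months after inclusion, so 20 Nov 2014. The 1 to 3 year window (20 Nov 2015 to 20 Nov 2017) holds rounds 2016 and 2017. The two-year point is 20 Nov 2016, which is 61 days from the 2017 round and 245 from the 2016 round, so 2017 is preferred.
- Latest inclusion, 30 Jun 2020: the baseline round is 2020. Follow-up can be 2022 or the part of 2023 up to 1 Feb. The two-year point is 30 Jun 2022, which is 102 days from the 2022 round and 204 from the 2023 round, so 2022 is preferred.
- Running every inclusion date through the same rules gives baseline rounds 2015-2020, preferred follow-up rounds 2017-2022, and any permitted follow-up round 2016-2023. The 2023 round is open only to inclusions from 20 Jan 2020 and is never the nearest to two years.

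**2. How large the bias could be.** All inputs here are assumptions. Let p0 = 0.35 be the risk of low well-being in earlier rounds, k = 1.3 or 1.6 the odds multiplier in later rounds, and s the share of a group answering in later rounds, with no intervention effect.

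- Later risk: p1 = k·o/(1 + k·o), with o = 0.35/0.65 = 0.538. This gives 0.412 for k = 1.3 and 0.463 for k = 1.6.
- Group risk: p0 + s(p1 − p0). The spurious odds ratio is the ratio of the two groups' odds.

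| Late shares | k | Group risks | Odds ratio |
|---|---|---|---|
| equal | any | equal | 1.00 |
| 50% v 30% | 1.3 | 0.381 v 0.369 | 1.05 |
| 50% v 30% | 1.6 | 0.406 v 0.384 | 1.10 |
| 60% v 20% | 1.3 | 0.387 v 0.362 | 1.11 |
| 60% v 20% | 1.6 | 0.418 v 0.373 | 1.21 |

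These are crude odds ratios, whereas models 1 and 2 both adjust for the inclusion outcome. Refitting the same scenarios with that adjustment, under an assumed latent correlation of 0.3 to 0.5 between a child's two answers:

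- If the shift affects both of a child's rounds, 1.05-1.10 becomes 1.04-1.08 and 1.11-1.21 becomes 1.08-1.17.
- If it affects the follow-up round only, there is no reduction, and the largest value is 1.24.

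**3. Cost under the plan's own cap.** Nine covariates need 9 × 10 = 90 observations of the rarer outcome; ten need 100. If parameters are counted instead (three-level education as two, group terms left out), the need is 100 now, 110 with linear year and 120 with three periods.

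**The case against.** The strongest reply is that the imbalance is conjecture. A reader might infer that group membership depends on when invitations were made, because children above the cut-off were invited and the reference children were not. The plan does not say so. It gives one inclusion window for the whole study and a BMI trigger, with no calendar rule. The structural difference it does document is place and data source, since the reference group comes from one municipal system. Non-invitation may reflect municipality rather than timing, and a calendar covariate would not address that.

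A reader might also infer that outcomes are compared across eight years. That is the outer limit for the whole cohort. Each child's follow-up lies 1 to 3 years after inclusion, and the preferred follow-up rounds cover 2017 to 2022. Figure 1 plots inclusion time against the DNWQ time points, so calendar structure is at least described. The figure is not reproduced, so whether it separates the groups cannot be judged.

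Finally, the magnitude rests wholly on assumed values, and the milder scenario is small. Adding a term also has a price: ranked last, it is the first to be dropped under the cap; ranked higher, it may displace a listed confounder.

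All of this stands, and it limits the point to a possibility that the plan leaves open. It does not remove the omission. No calendar term, period sensitivity analysis or tabulation by year is specified, and the details that would settle the question are absent.

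**Conclusion.** The point holds as a minor gap. Calendar time is missing from every covariate list in an unmatched observational comparison whose follow-up answers come from several annual rounds. Confounding of the between-group odds ratios by period cannot be excluded. The document does not establish that it is present, nor that the groups differ in calendar time.

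Under the assumed inputs, the bias in a crude odds ratio is about 5% to 21%. Adjustment for the inclusion outcome reduces it somewhat if the shift touches both of a child's rounds, and does not if it touches follow-up alone. It is nil when the groups have the same calendar mix.

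The point concerns the between-group models only. The McNemar tests compare a group with itself over time, so any age or period trend enters them directly and a covariate cannot remove it.

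**What to change.** 1. Define the index date for children who were never invited. Without it, neither their questionnaire windows nor their year of inclusion can be set. State also when each programme ran and why these children were not invited.
2. Add rows to Table 1 for inclusion year and follow-up DNWQ round by group. This costs no parameters and shows whether the concern is real.
3. Add calendar period, as linear year or as two to three grouped periods, to model 2 and to the models of Tables 5-7. State its rank in the priority order, for example directly after age. If the one-per-10 cap would make it displace a listed confounder, run it as a prespecified sensitivity analysis instead.
4. State in advance that if inclusion years barely overlap between two groups, their comparison is restricted to the overlapping years. Regression cannot separate period from group where there is no overlap.

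The variable is already in the data. Linear year or two periods costs one parameter and three periods cost two; a finer grouping would cost more. Counted as one covariate, the term raises the full model's requirement from 90 to 100 observations of the rarer outcome. Restriction to overlapping years would lose children. None of this repairs the within-group McNemar tests.
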